3.2 Visit Windows

The number of visits that occur before the first islet transplant will be determined by time on the waiting list and cannot be determined in advance. Screening tests and baseline measurements that are obtained during this period must be obtained within specified windows relative to the day of randomization, as described in Appendices 1 of the CIT-02 protocol. Following a transplant, up to 18 visits may be scheduled. The schedule of follow-up visits and their detailed activities are described in Appendix 1 and 2 of the CIT-02 protocol.

3.3 Study Population

The study population consists of individuals with T1D who meet the eligibility criteria for the trial described in Section 3 of the CIT-02 protocol. This section of the SAP describes three study populations. All efficacy analyses will be done on the Intent-to-Treat (ITT) population. Parallel analyses will be done on the per-protocol population. Safety analyses will focus on the safety population.

3.3.1 Intention to Treat Population

All efficacy and safety analyses will be based on a modified ITT principle: any subject in whom protocol-directed therapy (*e.g.*, immunosuppression) is initiated will be included in the ITT population. Subjects who are randomized but for whom a protocol-directed therapy is not initiated will be listed in the final study report but will not be included in the ITT population.

3.3.2 Per-Protocol Population

A per-protocol analysis will include all subjects who are randomized to Protocol CIT-02 and in whom the islet transplant procedure is initiated. The procedure will be considered initiated when the operator (*e.g.*, surgeon or interventional radiologist) has started the process of obtaining access to the portal vein (*i.e.*, entered the body with a needle or scalpel).

3.3.3 Safety Population

The safety population consists of any subject in whom protocol-directed therapy (e.g., immunosuppression) is initiated. Subjects in this population might not receive an islet transplant.

3.4 Treatment Assignment and Treatment Groups

3.4.1 Treatment Assignment

Enrolled subjects who meet the eligibility criteria will be placed on a waiting list for a transplant. Once a compatible pancreas becomes available, the subject will be reevaluated to ensure that s/he satisfies all inclusion/exclusion criteria and therefore is still eligible for participation in the CIT-02 study. Subjects will enter into the CIT-02 study via randomization between this study and the phase 3 study, Protocol CIT-07. Note that this randomization is between protocols and not to treatment arms within a protocol. The randomization is being performed to avoid bias in the assignment of subjects to protocols. The treating center will be blinded to protocol assignments until the subject is ready for transplantation.

3.4.2 Treatment Groups

The treatment in Protocol CIT-02 is the islet transplant and the accompanying immunosuppressive regimen, which includes LSF. This is a single-arm, open-label trial, and all subjects assigned to this protocol receive identical study treatment.

3.4.3 Center Pooling Method

The analysis of the primary endpoint assumes no between-center variability with regard to the favorable outcome resulting from the treatment. The data from both centers will be pooled without any adjustment for centers. Descriptive statistics will be tabulated across and within centers for all endpoints.

3.5 Subject Disposition

The number of subjects enrolled and treated will be summarized and reported in the following categories:

- a. The numbers of subjects who are screened total and grouped by center.
- b. The numbers of subjects who are excluded from study participation total and grouped by center. The numbers will also be tabulated by the reason for exclusion.
- c. The numbers of subjects who are enrolled (sign informed consent for screening) total and grouped by center.
- d. The numbers of subjects who are eligible for the transplant both after enrollment and before the transplant, grouped by center.
- e. The numbers of subjects who are lost to follow-up, grouped by center and reason. (The rules for premature termination of study treatment are fully described in Section 5.7.2 of the CIT-02 protocol).

A list of all enrolled subjects (grouped by center) who are prematurely terminated from the study (withdraw consent or are lost to follow-up) will be provided. The list will give subject identification, the specific reason for termination, immunosuppression regimen, and the duration of treatment before the termination.

3.6 Major Protocol Deviations

Major protocol deviations will be summarized by center and for the total study and grouped into the following categories:

- 1. Impacts the inclusion and/or exclusion criteria (PD1)
- 2. Involves consent violations (PD2)
- 3. Alters protocol-specified study therapy (PD3)
- 4. Impacts the ability of the Sponsor to evaluate the endpoints of the study (PD4)
- 5. Involves administration of prohibited medications (PD5)

Individual subjects with these protocol deviations will be listed with specifics regarding the deviation.

4 General Statistical Issues

4.1 Analysis Software

It is expected that the majority of analyses will be performed by SAS[®] Software (version 9.1 or later), R (version 2.5.1 or later), or S-Plus[®] (version 8 or later).

4.2 Derived and Computed Variables

It is expected that additional variables derived or computed from those listed in Section 2.3 will be required. The SAP will not be amended for additional variables. Any additional derived or computed variables will be identified and documented in the SAS programs that create the analysis files.

5 Demographic and Baseline Variables

Baseline data consists of demographic information and medical/physical assessments during the waiting period between enrollment and randomization. These data will be grouped into the following categories:

Demographic Variables

- Age
- Sex
- Race (White, Black, Hispanic, Asian, and other)

Baseline Diabetes Control Variables

- Insulin requirement
- HbA1c

- Fasting and post prandial plasma glucose
- Fasting and post prandial C-peptide
- Number of severe hypoglycemic events in the last year
- MAGE score
- LI
- Clarke Score
- HYPO Score
- β-score
- C-peptide/(glucose x creatinine) ratio

Body Habitus variables

- Body weight
- Height
- QOL Measures

5.1 Statistical Analysis of Baseline Data

Descriptive statistics for the baseline variables, collapsed over center, will be presented in summary tables.

Continuous variables will be summarized by mean, standard deviation, median and range. Categorical variables will be presented as enumerations and percentages. Because the number of subjects randomized in each center will be small, tests for statistically significant differences between centers will not be performed.

5.2 Statistical Analysis of Use of Medication

Concomitant medications will be coded according to the World Health Organization drug dictionary, and the number of subjects using each medication will be tabulated for each center. Results will be presented across centers and within centers.

5.3 Statistical Analysis of Study Completion

The number and percentage of subjects who complete the study, losses to follow-up, times to loss to follow-up, and reasons for loss to follow-up (*e.g.*, AEs) will be presented.

6 Efficacy Analyses

6.1 Statistical Analyses of Primary Endpoint

The primary endpoint for the study is the proportion of insulin-independent subjects at Day 75 (\pm 5 days) following the first islet transplant.

The primary analysis is designed to estimate the true rate of favorable outcomes at Day 75 in subjects in the ITT population pooled over both centers. The observed proportion of favorable outcomes out of the total number of subjects recruited will be used as the point estimate. A corresponding exact two-sided 95% confidence interval will be

constructed assuming an underlying binomial distribution for the target population as follows:

If *r* out of N total enrolled subjects achieve the favorable outcome, the lower bound of the exact 95% confidence interval is given by $p \ge p_L$ where p_L is the solution of the equation,

$$0.025 = \sum_{x=0}^{r} {N \choose x} p_{L}^{x} (1-p_{L})^{N-x}.$$

The upper bound of the exact 95% confidence interval is given by $p \le p_U$ where p_U is the solution of the equation,

$$0.025 = \sum_{x=r}^{N} {N \choose x} p_{U}^{x} (1-p_{U})^{N-x}.$$

This analysis will be conducted for the ITT population. The primary endpoint should be available for all treated subjects. Exception will be if a death occurs, if the subject withdraws consent to be followed, or if immunosuppression is begun but the subject never receives a transplant. In these cases, the endpoint will be classified as failure to achieve a favorable outcome. Should the endpoint not be evaluated for a particular individual for other reasons, a failure will be imputed unless an evaluation is done at a time later than 75 days after the first transplant but prior to a subsequent transplant, in which case the later value will be imputed. All imputations will be reported with the primary analysis.

There is no pre-defined minimum rate for efficacy in this study. Instead, an exact twosided 95% confidence interval is reported.

6.2 Statistical Analyses of Secondary Endpoints

Except for the primary analyses, there are no explicit or implied hypotheses in the protocol. Changes in the secondary outcomes are of interest as they will relate to efficacy as measured by the primary outcome variable. All analyses are descriptive and are intended to document the changes in these important variables, but are not intended to be used explicitly for making a decision for the efficacy of islet transplantation in this population.

6.2.1 Statistical Analyses of Secondary Endpoints

As discussed in Section 2.3.2.2, the additional efficacy endpoints are generally summarized at baseline (the most recent value prior to transplant), at 75 days and 365 days following the initial islet transplant, and again at 75 days, 365 days, and 730 days following the final islet transplant. Any variables that deviate from this schedule, as indicated by the Schedule of Events (Appendix 1 of the CIT-02 protocol) will be summarized accordingly. Imputations are not performed for missing values in the additional efficacy endpoints. Continuous secondary endpoints will follow analysis

template 1 (AT1) below. Categorical secondary endpoints will follow analysis template 2 (AT2) below.

Analysis Template 1 (AT1): For continuous data, the mean, standard deviation, minimum and maximum for the endpoint under consideration will be reported across centers and within centers. A 95% confidence interval will be constructed for the mean at each appropriate time point using the usual large sample theory. For example, let \bar{x} be the mean of the continuous variable and let s^2 be the corresponding sample variance. Then the 95% confidence interval shall be constructed as

$$\bar{x} \pm t_{0.025}^{n-1} \times \frac{s}{\sqrt{n}}$$

where t is from the t-distribution with n - 1 degrees of freedom and n is the size of the sample collected for the endpoint at the timepoint of interest.

Two additional analyses will also be conducted. First, changes from baseline to each time point will be assessed via the Wilcoxon Signed-Rank Test. Second, the mean, standard deviation, minimum, and maximum change from 75 days to 365 days following the final islet transplant will be summarized as well. The latter will also be accompanied by a 95% confidence interval to be calculated in the same fashion as above, but with the mean of the individual changes, \bar{d} , and the corresponding sample variance of the individual changes, s_d^2 , replacing the mean at any given time point, \bar{x} , and the associated sample variance, s^2 .

Analysis Template 2 (AT2): For categorical variables, the proportion of subjects with the characteristic under consideration (*e.g.*, the proportion who are women) will be reported, pooled across centers. A corresponding exact two-sided 95% confidence interval will be constructed for the proportion at each time point. Calculation of the 95% confidence interval follows the same process described for the primary endpoint in Section 6.1 above. McNemar's test for paired binomial data will be used to assess changes from baseline to each time point.

7 Safety Analyses

Safety analyses will be conducted for the safety population. Summaries will be prepared for the targeted safety endpoints listed in the secondary endpoints and for all observed AEs organized by body system. The CIT consortium modified the National Cancer Institute (NCI) toxicity table to create a document relevant for trials of adult pancreatic islet transplantation. The resulting reference manual, "Terminology Criteria for Adverse Events (TCAE) In Trials of Adult Pancreatic Islet Transplantation" (*CIT-TCAE*), provides descriptive terminology and a grading (severity) scale which will be utilized for adverse event (AE) reporting.

Regular safety analyses will be prepared for the Data and Safety Monitoring Board (DSMB). These summaries will be used to monitor the overall safety profile of the study. These analyses will summarize all AE data that are available at the time of the DSMB meeting. Analyses will summarize AEs by MedDRA preferred term and body

system. Separate incidence summaries will be prepared for serious AEs, for non-serious AEs, and for all AEs combined. Separate tables will summarize severity and attribution for SAEs. Each SAE could be attributed to the investigational agent (allogeneic islets/transplant procedure), the immunosuppression, both, or neither. Identical safety summaries will be included in the final statistical report.

The protocol also describes targeted safety endpoints. The planned analyses for general safety outcomes and for these targeted safety endpoints are described in the following sections.

7.1 Adverse Events

An AE is any occurrence or worsening of an undesirable or unintended sign, symptom (including an abnormal laboratory finding), or disease that is temporally associated with the use of a medicinal product whether considered related to the medicinal product or not. An SAE is defined as any AE occurring at any dose that suggests a significant hazard, contraindication, side effect, or precaution. This includes but is not limited to any of the following events (21CFR§312.32):

- Death.
- A life-threatening event. A life-threatening event is any adverse therapy experience that, in the view of the investigator, places the patient or participant at immediate risk of death from the reaction as it occurred.
- Inpatient hospitalization or prolongation of existing hospitalization.
- Persistent or significant disability.
- Congenital anomaly or birth defect.
- An event that required intervention to prevent permanent impairment or damage. An important medical event that may not result in death, be life threatening, or require hospitalization may be considered an SAE when, based on appropriate medical judgment, it may jeopardize the participant and may require medical or surgical intervention to prevent one of the outcomes listed above.
- Other conditions specified in the protocol.

In addition, events that occur at a higher than expected frequency, as determined by appropriate medical judgment, may be considered SAEs.

AEs will be graded on a scale from 1 to 5 according to the following standards in the *CIT-TCAE* manual:

Grade 1 = Mild adverse event.

Grade 2 = Moderate adverse event.

Grade 3 = Severe and undesirable adverse event.

Grade 4 = Life-threatening or disabling adverse event.

Grade 5 = Death.

AEs not included in the *CIT-TCAE* listing will be recorded and graded 1 to 5 according to the General Grade Definition provided as in the table below:

Grade	Description	Definition
		Transient or mild discomforts (<48 hours); no or minimal
Grade 1	Mild	medical intervention/therapy required; hospitalization not
		necessary (non-prescription or single-use prescription
		therapy may be employed to relieve symptoms [e.g.,
		aspirin for simple headache, acetaminophen for post-
		surgical pain]).
		Mild to moderate limitation in activity; some assistance
Grade 2	Moderate	may be needed; no or minimal intervention/therapy
		required; hospitalization possible.
		Marked limitation in activity; some assistance usually
Grade 3	Severe	required; medical intervention/therapy required;
		hospitalization possible.
		Extreme limitation in activity; significant assistance
Grade 4	Life-	required; significant medical/therapy intervention
	threatening	required; hospitalization or hospice care probable.
Grade 5	Death	Death.

 Table 1: General Severity Definition of Adverse Event

All AEs will be reported and graded whether they are or are not related to disease progression or treatment. The relationship of an SAE to islet transplantation, which includes the transplant procedure and/or the islet product, to the immunosuppression and/or infection prophylaxis, or to the secondary investigational agent will be defined by using the descriptors provided in Table 3.

Cala						
Code	Description	Definition				
UNRELATED CATEGORY						
1	Unrelated	This adverse event is clearly not related to allogeneic				
		islets, the islet transplant procedure, immunosuppression				
		or infection prophylaxis, or secondary investigational				
		agent.				
RELATED	CATEGORIES					
2	Unlikely	The adverse event is doubtfully related to allogeneic				
		islets, the islet transplant procedure, immunosuppression				
		or infection prophylaxis, or secondary investigational				
		agent.				
3	Possible	The adverse event may be related to allogeneic islets, the				
		islet transplant procedure, immunosuppression or				
		infection prophylaxis, or secondary investigational agent.				
4	Probable	The adverse event is likely related to allogeneic islets, the				
		islet transplant procedure, immunosuppression or				
		infection prophylaxis, or secondary investigational agent.				
5	Definite	te The adverse event is clearly related to allogeneic islets,				
		the islet transplant procedure, immunosuppression or				
		infection prophylaxis, or secondary investigational agent.				

Table 2: Attribution of Adverse Event

The collecting and recording procedures for AEs are described in detail in Section 8.3 of CIT-02 protocol.

7.2 Analysis of Secondary Endpoints for Safety Endpoints

The secondary safety endpoints described in Section 4.1.2.2 of the CIT-02 protocol target AEs related to islet transplantation (transplant procedure and/or islet product) and the immunosuppression and/or infection prophylaxis.

The targeted AEs related to the islet transplantation include:

- 1. AE-IP-1: Bleeding (>2 g/dL decrease in hemoglobin concentration)
- 2. AE-IP-2: Segmental portal vein thrombosis
- 3. AE-IP-3: Biliary puncture
- 4. AE-IP-4: Wound complication (infection or subsequent hernia)
- 5. AE-IP-5: Increased transaminase levels (>5 times ULN)

The targeted AEs related to the immunosuppression or infection prophylaxis therapy or related to the secondary investigational agent include:

- 1. AE-IIP-1: Allergy
- 2. AE-IIP-2: Reduction in GFR
- 3. AE-IIP-3: Increase in urinary albumin excretion
- 4. AE-IIP-4: Addition or intensification of anti-hypertensive therapy
- 5. AE-IIP-5: Addition or intensification of anti-hyperlipidemic therapy
- 6. AE-IIP-6: Oral ulcers

- 7. AE-IIP-7: Lower extremity edema
- 8. AE-IIP-8: Gastrointestinal toxicity
- 9. AE-IIP-9: Neutropenia, Anemia, or Thrombocytopenia
- 10. AE-IIP-10: Viral, Bacterial, or Fungal Infections
- 11. AE-IIP-11: Benign or Malignant Neoplasms

Other safety endpoints include:

- Incidence of the change in the immunosuppression drug regimen
- Incidence of immune sensitization defined by the presence of anti-HLA antibodies absent prior to transplantation

7.2.1 Safety Analyses from Randomization through Day 365 Following First Transplant

From randomization through Day 365 following the initial islet transplant, the incidence rates for each type of AE, grouped by severity, will be reported. For each type of AE, the number of resolved events will be counted as well. The mean, median, standard deviation, and range for the number of days until the AE is resolved will be calculated. Moreover, we will also report SAEs categorized by attribution; that is, SAEs related to the islet transplant procedure, immunosuppression, or LSF.

The incidence rate of a change in immunosuppression regimen (if applicable) will be reported. The exact two-sided 95% confidence interval of the incidence rate will also be reported.

The incidence rate of immune sensitization, defined as detection of anti-HLA antibodies (if applicable), will be reported. The exact two-sided 95% confidence interval of the incidence rate will also be reported.

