3.1 Study Period

The study period of this trial is a 24-month follow-up visit after the final islet transplant. Subjects may undergo up to 3 transplants in the course of this study; the final transplant must occur not later than 8 months following the first transplant.

In the first period, individuals who meet the general inclusion criteria will be approached regarding participation in the study. After informed consent has been obtained, they will be formally enrolled into the study. Eligibility will be confirmed based on the results of the screening visit procedures detailed in the study Schedule of Events (Appendix 1 of the CIT-02 protocol). Enrolled subjects who meet the eligibility screening for the studies will be put on the waiting list for an islet transplant.

Once a compatible islet preparation becomes available, a subject's eligibility will be reconfirmed, and eligible subjects who are randomized to Protocol CIT-02 will begin immunosuppression therapy on Day 0 (Day 0 is defined as the day of transplant).

During the post-transplant follow-up period, subjects may receive up to two additional transplants. After receiving his/her initial islet transplant, if a subject does not meet the criteria for insulin independence described in the Study Definitions section of the CIT-02 protocol, but has either a basal or stimulated C-peptide level ≥ 0.3 ng/mL (0.1 nmol/L), s/he will be considered for a second islet transplant. A second islet transplant will be

considered after day 85, but before 8 months after the first islet transplant and when all required metabolic assessments are complete. If, after the second islet transplant, both basal and stimulated C-peptide levels remain <0.3 ng/mL (0.1 nmol/L), the recipient will be considered to have failed the endpoint, and immunosuppression will be managed as described in the protocol. A third islet transplant will be considered only if all the criteria described in Section 7.6.2 of the CIT-02 protocol are met. Islet transplant recipients who have completed 8 months of follow up after their first infusion will no longer be eligible for additional islet transplants under the CIT-02 protocol. The number of excluded subjects and the number of protocol violations will be noted throughout the duration of the study.

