7.2.2 Safety Analyses from Randomization through All of Follow-up

The analyses described in Section 7.2.1 above will be performed again for the entire duration of the study.

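### Days to AE resolution are summarised with no rule for AEs still open, so on the natural reading the durations of persistent AEs are understated

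*SAP*

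**What the plan says.** SAP Section 7.2.1 opens with incidence: "From randomization through Day 365 following the initial islet transplant, the incidence rates for each type of AE, grouped by severity, will be reported". It then adds a count, "For each type of AE, the number of resolved events will be counted as well", and a duration summary, "The mean, median, standard deviation, and range for the number of days until the AE is resolved will be calculated". Section 7.2.2 extends all of this to full follow-up: "The analyses described in Section 7.2.1 above will be performed again for the entire duration of the study".

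Follow-up is bounded by Section 3.1: "The study period of this trial is a 24-month follow-up visit after the final islet transplant", and "the final transplant must occur not later than 8 months following the first transplant".

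The SAP does not say how an AE without a resolution date enters the duration summary. It names no censoring, no survival estimate and no end-date convention. Section 7.1 refers to the protocol for collecting and recording AEs, not for this analysis. Section 7.2.3 allows for unequal follow-up when it models incidence per 100 person-days, but durations get no such treatment.

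**The concern.** A number of days until resolution exists only for an event that has resolved. An AE still open when observation ends is right-censored: its duration is known only to exceed the time observed. Long durations are more likely to be cut off than short ones, so a plain mean or median of the completed durations is biased short.

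Some targeted AEs in Section 7.2 can plausibly outlast the window, for example "AE-IIP-2: Reduction in GFR". The same list has increased urinary albumin excretion, added anti-hypertensive or anti-hyperlipidemic therapy, and neoplasms. AEs that begin after a second or third transplant also have less time to resolve before Day 365.

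What is at stake is how the safety table reads. Persistent toxicities would appear nearer in duration to transient ones than they are. The number resolved, printed alongside, shows that events are missing from the summary but does not correct it.

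**Working it through.** The SAP states no figure for AE duration, so there is none to reproduce. The check is of direction and size under stated assumptions.

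**Inputs from the SAP.** The first window ends at Day 365 (Section 7.2.1). Whole-study follow-up runs 24 months past the final transplant, which falls at most 8 months after the first (Section 3.1). That is about 730 days from first transplant with one transplant, and up to about 730 + 243 = 973 days with more.

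**Assumptions, not in the SAP.** Durations D are exponential with mean m. Onset is uniform over 0 to A days, where A is either the whole window or the first 30 days. There is no early loss to follow-up.

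**Formula.** An AE counts as resolved if onset + D ≤ W, where W is the cut-off. When onset is uniform over the whole window (A = W):

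- P(resolved) = 1 − (m/W)(1 − e^(−W/m))
- Mean among resolved = [m − 2m²/W + (m + 2m²/W) e^(−W/m)] / P(resolved)

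For m = 260 and W = 365, e^(−W/m) = 0.2457 and 2m²/W = 370.4.

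- P(resolved) = 1 − 0.7123 × 0.7543 = 0.463
- Mean = [260 − 370.4 + 630.4 × 0.2457] / 0.463 = 44.5 / 0.463 ≈ 96 days

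In the other cases each duration d is weighted by the chance that it completes in time, min(1, (W − d)/A), and the mean is taken by numerical integration.

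**Reported mean among resolved events (share resolved)**

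| Onset; cut-off | True mean 43 | True mean 130 | True mean 260 |
|---|---|---|---|
| Uniform to 365; Day 365 | 37 (88%) | 76 (67%) | 96 (46%) |
| First 30 days; Day 365 | 43 (100%) | 105 (93%) | 137 (74%) |
| Uniform to 730; Day 730 | 40 (94%) | 103 (82%) | 153 (67%) |
| Uniform to 973; Day 973 | 41 (96%) | 110 (87%) | 177 (74%) |
| Uniform to 365; Day 730 | 43 (100%) | 120 (98%) | 183 (87%) |

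The last row is the mildest reading: AEs that start by Day 365 keep a resolution date found later, up to Day 730.

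**Medians.** For a true mean of 260 the true median is 260 × ln 2 = 180 days. The resolved-only median in the Day-365 window with uniform onset is 77 days.

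**If open AEs are instead closed at the cut-off.** The mean of min(D, W − onset) for m = 260, uniform onset and Day 365 is about 120 days, which is also short.

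**Whether censoring repairs it.** In simulation (Day-365 window, uniform onset) with open AEs censored at Day 365, a true median of 124.8 days gives a Kaplan-Meier median of 125.8, against 67.7 among resolved events. For a true median of 253.0 the figures are 261.5 and 84.4.

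**The case against.** **The text does not say that only resolved events are averaged.** That is correct; it is an inference. It is the natural reading, because the sentence follows directly on the count of resolved events. The main alternative, closing open AEs at the cut-off, is also biased short. With neither rule written down, the programmer would have to choose.

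**The Day-365 limit may apply only to incidence.** This stands in part. The phrase on Day 365 sits in the incidence sentence, and nothing says that a later resolution date is discarded. If such dates are used, the reported mean for a true mean of 260 is 183, not 96. The bias shrinks but remains.

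**The size is assumed.** This stands. The exponential form, the means and the onset patterns are not in the SAP. For brief AEs the bias hardly matters: a true mean of 14 days is reported as 13.4 in the Day-365 window with uniform onset. Early onset helps too: with onset in the first 30 days, a true mean of 60 is reported as 59. It does not protect AEs lasting many months.

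**A reader might infer that the most persistent toxicities would look the shortest-lived.** The figures do not support this. Within each row of the table the reported mean rises with the true mean. Contrasts are compressed, not reversed.

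**The stakes are limited.** This also stands. The summary is descriptive, in a 12-subject single-arm pilot (Section 2.4). AE duration is not among the safety endpoints listed in Section 2.3.2.3, and the stopping rules in Section 8.1 rest on the primary endpoint. The number resolved is printed alongside incidence.

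**Kaplan-Meier has its own difficulties.** Repeated AEs within a subject are not independent, death is not ordinary censoring, and some AE types, such as added anti-hypertensive therapy, have no evident resolution. These points shape the remedy but do not remove the need for a rule.

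**Conclusion.** The point holds as a minor one. Sections 7.2.1 and 7.2.2 specify a plain summary of days to resolution and leave open AEs without a rule. Each workable reading understates the duration of persistent AEs.

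For a true mean of 260 days the reported mean lies between about 96 and 183 days in the uniform-onset scenarios, depending on the window and on whether later resolution dates are used. A twofold true difference (130 against 260) appears as 76 against 96 in the Day-365 window, a ratio of 96/76 ≈ 1.3. These sizes rest on exponential durations and assumed onset; the direction needs only that longer AEs are more often still open when observation ends.

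A reader should not conclude that the SAP states a resolved-only rule, or that durations will be halved as a matter of course. Nor does the point touch the primary endpoint or any stopping decision.

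**What to change.** Add to Section 7.2.1, and carry into Section 7.2.2:

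- AEs without a resolution date are right-censored at the end of the window or at last contact, whichever is earlier. State whether a resolution after Day 365 counts for an AE that began by Day 365.
- Death with an AE open is treated as a competing event or reported separately.
- For AE types with enough events, report the Kaplan-Meier median time to resolution. Any confidence interval allows for repeated events within a subject.
- For every AE type, report the number still ongoing beside the number resolved.
- Any retained mean, SD, median or range of observed days is labelled as among resolved events.

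The cost is a few lines of SAP text and routine programming on dates that the planned summary already needs. The downside is that with few events some medians will be imprecise or not reached. For those AE types the label and the ongoing count are enough.
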